## 7. STUDY DESIGN

### 7.1. Overview of Study Design

Protocol STP206-002 is designed as a multi-center, randomized, double-blind, placebo-controlled study. This will be a dose escalation study to determine safety and tolerability of two doses of STP206 versus control in four sequentially decreasing birth weight strata.

[figure not shown]
Neonates for whom informed consent is obtained and who meet eligibility criteria will be eligible to enroll in this study. All neonates enrolled in the study will be randomized and will receive daily doses of blinded study treatment (STP206 or control) for between 2 and 11 weeks with the duration of dosing based upon gestational age at birth. All neonates enrolled in the study will be placed under Universal Precautions and all study personnel with subject contact are trained in appropriate NICU infection control practices.

- The doses of STP206 to be administered are:
  - Low dose STP206: approximately 1 billion ( $1 \times 10^9$ ) CFU of [REDACTED] and approximately 100 million ( $1 \times 10^8$ ) CFU of [REDACTED] (total of 1.1 billion CFU)
  - High dose STP206: approximately 9 billion ( $9 \times 10^9$ ) CFU of [REDACTED] and approximately 900 million ( $9 \times 10^8$ ) CFU of [REDACTED] (total of 9.9 billion CFU)
- Neonates will be stratified into the following four birth weights: 2000-1501 g, 1500 to 1000 g, 999 to 750 g, and 749 to 500 g.
- Within each birth weight strata, subjects will be randomized to the STP206 low dose or control group followed by the STP206 high dose or control group, resulting in the following eight study groups:
  - Study Group 1a – Birth weight 2000 to 1501 g and Low dose STP206 versus control
  - Study Group 1b – Birth weight 2000 to 1501 g and High dose STP206 versus control

- Study Group 2a – Birth weight 1500 to 1000 g and Low dose STP206 versus control
- Study Group 2b – Birth weight 1500 to 1000 g and High dose STP206 versus control
- Study Group 3a – Birth weight 999 to 750 g and Low dose STP206 versus control
- Study Group 3b – Birth weight 999 to 750 g and High dose STP206 versus control
- Study Group 4a – Birth weight 749 to 500 g and Low dose STP206 versus control
- Study Group 4b – Birth weight 749 to 500 g and High dose STP206 versus control
- Each birth weight strata/STP206 dose group will consist of 12 subjects.
- Within each birth weight strata/STP206 dose group, subjects will be randomized in a 2:1 ratio to either the STP206 or control group.

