## 8.4. Preparation for Administration

### 8.4.1. STP206

Each vial of STP6 [REDACTED] and STP11 [REDACTED] will be reconstituted using with 1.0 mL of water for injection of USP quality in the research pharmacy (Note: STP206 must not be reconstituted at the subject's bedside). The appropriate volume of the reconstituted bacterial suspension will be removed from STP6 and STP11 vials by sterile syringes and stored in the individual syringes until administered. The reconstituted STP206 must be administered within 2 hours following reconstitution.

The following dose volumes will be administered:

- For the low dose of STP206, 0.1 mL of STP6 and 0.1 mL STP11 will be drawn up for administration (0.2 mL total).
- For the high dose of STP206, 0.9 mL of STP6 and 0.9 mL of STP11 will be drawn up for administration (1.8 mL total).

The syringes with the reconstituted STP206 will be labeled with the protocol number, subject identification (randomization number and initials), date and time of preparation, dose volume, and the words "contains STP6 or vehicle" [REDACTED] or "contains STP11 or vehicle" [REDACTED].

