### 8.4.2. Control

Syringes containing the matching volume of vehicle for both STP6 and STP11 will be used as the control. Syringes will be labeled in the same manner as syringes with STP206 to maintain study blinding.

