#### *13.2.3.1. Efficacy Data Analysis*

The following efficacy parameters will be compared between those who received STP206 vs. control:

- Feeding intolerance
- Death
- NEC incidence
- Incidence of sepsis
- Incidence of other neonatal complications of prematurity (ROP, IVH, BDP, etc)

Details regarding the analysis of efficacy data will be provided in the SAP.

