8.6 Analysis of Efficacy Parameters

Descriptive summaries will consist of frequencies and percentages for categorical measures and of the number of subjects [N], mean, standard deviation [SD], median, 25th and 75th quartiles, minimum [min], and maximum [max] values for continuous measures. Descriptive summaries will be presented for each treatment group, BW strata, and all BW strata combined.

The incidence rates of the exploratory variables for those who received STP206 vs. control will be summarized and displayed.

The analyses of efficacy variables will be performed for ITT population only.

Efficacy will be displayed by (i) dose group and BW stratum and (ii) by all BW strata combined for STP206 low dose, STP206 high dose and control group.

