8.6.2 Analysis of Secondary Efficacy Variables

8.6.2.1 Endpoints

- Incidence of suspected NEC (Stage I)
- Incidence of confirmed NEC (Stage II and higher)
- Incidence of sepsis/bacteremia
- Incidence of feeding intolerance
- Hospital Mortality (death occurred during inpatient hospitalization)
- Incidence of other neonatal complications of prematurity
 - ROP
 - IVH
 - BDP
 - Spontaneous Gastrointestinal Perforation
 - Patent ductus arteriosus requiring treatment with indomethacin, ibuprofen or surgery

The incidence rate of each outcome will be summarized separately. The secondary efficacy will be displayed by (i) dose group and BW stratum and (ii) by all BW strata combined for STP206 low dose, STP206 high dose and control group. Incidence rate of suspected NEC (stage I), confirmed NEC (stage II and higher) will be further summarized by two subgroups: gestational age at birth is less than and equal to 28 weeks, and greater than 28 weeks.

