8.7 Analysis of Safety

Safety population will be used for the analysis of Safety.

Safety data will be displayed by (i) dose group and BW stratum and (ii) by all BW strata combined for STP206 low dose, STP206 high dose and control group.

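### The all-strata displays set both doses beside one control group that pools low-volume and high-volume controls from separately randomised cohorts, so any volume or calendar-time effect would be mixed into the dose contrasts and hidden

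*SAP*

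**What the plan says.** **Design.** There are four birth-weight strata, each with a low-dose cohort followed by a high-dose cohort, so eight cohorts of 12. Protocol 7.1 states: "Within each birth weight strata/STP206 dose group, subjects will be randomized in a 2:1 ratio to either the STP206 or control group". A cohort opens only after the DSMC has reviewed the one before it. Recruitment runs for about four years (Protocol 7.1.3).

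**Control treatment.** Protocol 8.4.2 states: "Syringes containing the matching volume of vehicle for both STP6 and STP11 will be used as the control". Under Protocol 8.4.1 the low dose is 0.1 mL of each component, 0.2 mL in all. For the high dose, "0.9 mL of STP6 and 0.9 mL of STP11 will be drawn up for administration (1.8 mL total"). Controls in low-dose cohorts therefore receive 0.2 mL of water and controls in high-dose cohorts 1.8 mL.

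**Analysis.** SAP 8.6 lays out display (ii) "by all BW strata combined for STP206 low dose, STP206 high dose and control group". SAP 8.6.2.1 states: "The secondary efficacy will be displayed by (i) dose group and BW stratum and (ii) by all BW strata combined". SAP 8.7 says the same of safety: "Safety data will be displayed by (i) dose group and BW stratum and (ii) by all BW strata combined". In both, display (ii) has three columns: low dose, high dose and one control group. SAP 8.1 (disposition) and 8.4 (baseline) use the same columns. SAP 7.2 plans no covariate adjustment. Protocol 13.2.3.1 says that the efficacy parameters "will be compared between those who received STP206 vs. control".

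**The concern.** A vehicle control matched in volume lets a reader attribute a difference within a cohort to the organisms and not to the fluid or the period. Pooling the two sets of controls gives up that matching, in opposite directions for the two doses.

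The outcomes that could plausibly respond to volume are among the planned endpoints. Feeding intolerance is judged partly on abdominal distension (Protocol 10.5.1), and suspected NEC (Stage IA) includes gastric residuals, distension and emesis (Protocol Appendix B). The protocol itself lets the daily dose be divided in volume-restricted infants (Protocol 10.8.1).

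In a two-dose escalation study, the all-strata table is where readers will look for a dose pattern. With one control column they cannot tell whether a rise from low to high dose is matched by a rise in the controls.

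**Working it through.** **1. Volumes.** 0.1 + 0.1 = 0.2 mL and 0.9 + 0.9 = 1.8 mL, which reproduces Protocol 8.4.1. The ratio is 1.8/0.2 = 9, the same as the CFU ratio 9.9/1.1 = 9. Dose and volume are therefore fully confounded among STP206 infants. Only the controls carry separate information on volume.

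**2. Composition of the columns.** Eight cohorts of 12 at 2:1 give 8 STP206 and 4 control each.
- Low dose: 4 × 8 = 32. High dose: 4 × 8 = 32.
- Controls: 4 × 4 = 16 from low-dose cohorts and 16 from high-dose cohorts, 32 pooled.
- Beside each dose, 16 of 32 controls were randomised in other cohorts and given the other volume.

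This is the planned total of 96. The protocol expects about 100 to 110 enrolled, so the realised split will be close to this but not exact.

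**3. Volume against feeds** (suggested feeds, Protocol 10.6.1).
- 500 g at 20 mL/kg/day: 10 mL, so 0.2 mL is 2% and 1.8 mL is 18%.
- 749 g at 20 mL/kg/day: 14.98 mL, so 1.8 mL is 12%.
- 2000 g at 20-40 mL/kg/day: 40-80 mL, so 1.8 mL is 2.25-4.5%.
- 500 g at the later target of 140 mL/kg/day: 70 mL, so 1.8 mL is 1.8/70 = 2.6%.

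**4. Effect on the contrasts.** Let the risk be p in low-dose cohorts and p + d in high-dose cohorts, with no organism effect. The pooled control risk is (16p + 16(p + d))/32 = p + d/2.
- Low dose minus pooled control: -d/2.
- High dose minus pooled control: +d/2.
- Each dose minus its own cohorts' controls: 0.

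The documents give no rates. With p = 20% assumed:

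| d (points) | Pooled control | Low dose | High dose | Own-cohort contrasts |
|---|---|---|---|---|
| 5 | 22.5% | -2.5 | +2.5 | 0, 0 |
| 10 | 25% | -5 | +5 | 0, 0 |
| 20 | 30% | -10 | +10 | 0, 0 |

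The shifts do not depend on p. A calendar-time difference averaging d between low-dose and high-dose cohorts acts in the same way.

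**5. Precision.** The standard-error factor is √(1/32 + 1/16) = 0.306 with own-cohort controls and √(1/32 + 1/32) = 0.250 with pooled controls. The ratio is 1.22.

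Root mean squared error (RMSE) weighs bias against precision, still with p = 20%.
- d = 10. The pooled-control variance is (16 × 0.16 + 16 × 0.21)/32² = 0.0058. Low dose, pooled: √(0.16/32 + 0.0058 + 0.05²) = 11.5 points; own: √(0.16 × 0.09375) = 12.2. High dose, pooled: √(0.21/32 + 0.0058 + 0.05²) = 12.2; own: √(0.21 × 0.09375) = 14.0.
- d = 20. The pooled-control variance is (16 × 0.16 + 16 × 0.24)/32² = 0.00625. Low dose, pooled: √(0.16/32 + 0.00625 + 0.10²) = 14.6; own: 12.2. High dose, pooled: √(0.24/32 + 0.00625 + 0.10²) = 15.4; own: √(0.24 × 0.09375) = 15.0.

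**6. All STP206 v all control.** Both groups are half low-volume (32 of 64; 16 of 32), so d cancels. With 2:1 in every cohort the Mantel-Haenszel weight is (2N/3)(N/3)/N = 2N/9, proportional to cohort size N. The stratified estimate then equals the crude one, so stratifying costs nothing here and protects if the realised ratios drift.

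**The case against.** Several stronger readings are tempting, and the documents do not support them.

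- **That the plan never separates controls by cohort.** Display (i) is by dose group and stratum. Protocol 7.1 uses a similar term for a cohort that includes its own controls, and SAP 7.3 counts evaluable subjects in the same units. Display (i) may well show each cohort beside its concurrent, volume-matched controls. The SAP does not say so, and the table shells are in a separate document (SAP 11). If it does, each cell has only 4 controls, which is why display (ii) will carry most of the reading.
- **That a false dose response will appear, or that controls received a wrong volume.** No volume effect is shown anywhere in the documents. Each control receives the volume that its own cohort requires. The 18% figure is the lightest permitted infant at the starting feed, and dividing the dose limits the bolus. The raw gap between the two STP206 columns would also exist whatever was done with the controls; the pooled column only fails to explain it.
- **That no STP206 v control view exists.** SAP 8.6 gives one for the exploratory variables, which SAP 8.6.5 lists as suspected NEC, sepsis and antibiotic use. SAP 8 allows further pooled analyses of clinical events if judged necessary. What is missing is that column in the stated layout for secondary efficacy and safety.

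The precision argument also stands. At an assumed d of 10 points the pooled control has the smaller RMSE for both doses; at 20 points the order reverses. Which control should lead a dose contrast is a bias-variance choice. Finally, the summaries are descriptive, comparisons are exploratory (SAP 7.1), and the DSMC reviews data for each dose/birth-weight group (SAP 7.4.2), so nothing here shows that escalation decisions would be affected.

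**Conclusion.** The point holds as a gap in presentation, not as an analysis error. In display (ii), half of the controls beside each dose (16 of 32 at planned size) are non-concurrent and received a volume that differs ninefold. Any volume or period effect d would enter as -d/2 for the low dose and +d/2 for the high dose, and the layout would not let a reader see it.

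The size of d is unknown. The 5 to 20 point range is an assumption, and a volume mechanism is most plausible in the lightest infants early in feeding. The harm at stake is a misleading descriptive dose pattern, not a false confirmatory claim.

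The result assumes all eight cohorts complete. Protocol 7.1 allows the high dose to stop while low-dose cohorts continue. If that happened after the second stratum, 16 high-dose infants from the two heavier strata would sit beside 16 + 8 = 24 controls drawn from all four, and birth weight would be mismatched as well.

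**What to change.** Amend SAP 8.6, 8.6.2.1 and 8.7, and the matching table shells, as follows.

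1. State that display (i) shows each cohort's STP206 infants beside that cohort's own controls.
2. In display (ii), keep the pooled control column and add two columns beside it, *control, low-dose cohorts* and *control, high-dose cohorts*. Do this at least for feeding intolerance, suspected and confirmed NEC, and adverse events. Show each dose against its own cohorts' controls and against the pooled control.
3. Add an all-STP206 v all-control risk difference, stratified by the eight cohorts (Mantel-Haenszel), with a 95% confidence interval labelled exploratory.

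This needs no new data and no change in conduct. The cost is SAP wording and two or three more columns. Own-cohort dose contrasts have a standard error about 22% larger than pooled ones, which is why both should be shown. With 4 controls per cohort, the interval in item 3 will be wide and should be read as descriptive.

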2.3 Target Population and Study Rationale

The target population for intended clinical use of STP206 is premature VLBW infants (1500 to 1001 g) and ELBW infants (1000 to 500 g) who are at risk of developing NEC.

The hypothesis is, therefore, that influencing the intestinal flora by the administration of probiotics can provide a balance between beneficial and pathogenic bacteria, modulate the pro-inflammatory response, and enhance intestinal maturation; thus, possibly reducing the incidence of NEC. This hypothesis is supported by the clinical trials (see Section 5.3.2.2 of the protocol) conducted with probiotics to date. These published clinical studies conducted in neonates  suggest that supplementation of VLBW infants with STP206 may have clinical use in the prevention of NEC.

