- Enrollment of neonates into study groups will occur sequentially. Enrollment into the high dose group within a BW stratum will not proceed until after the safety data from the low dose group is reviewed by the study independent Data Safety Monitoring Committee (DSMC). Similarly, enrollment into the next lower BW stratum will not proceed until the safety data from the high dose group of the prior weight stratum is reviewed by the study independent DSMC. If, at any point during the study the DSMC determines that the high dose of STP206 is not safe and well tolerated, weight de-escalation will continue with the low dose of STP206.

The sequencing of treatment groups of the study is shown in Figure 1. Enrollment will begin with neonates weighing 2000 - 1500 g at the low dose of STP206 (Group 1a). Safety data through the last dose of blinded study treatment will be evaluated by the DSMC (see Protocol Section 7.7). Subsequent cohorts will not open for enrollment before the data from the previous cohort has been reviewed by the DSMC. If the safety data review conducted by the DSMC determines there are no safety concerns, study groups will open sequentially as illustrated in the figure below.

Figure 1 – Treatment Group Sequence

Following completion of blinded study treatment dosing, neonates will be evaluated at 1 week, 1 month, 3 months, and 6 months for safety and growth assessments.

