4.3 Method of Assignment of Subjects to Treatment Groups

Neonates enrolled into the study will be randomized to receive either STP206 or control in a 2:1 ratio based upon a pre-prepared, computer generated, centralized randomization schedule. To assure a balance in BW among treatment groups, randomization will be stratified by BW in four strata: 2000-1501g, 1500 to 1000 g, 999 to 750 g and 749 to 500 g.

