7.2 Adjustments for Covariates

Not applicable to this study.

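### If the high dose is dropped part-way, or the study stops between dose cohorts, the crude combined dose columns lose their shared birth-weight mix: an inert high dose is expected to look better than control, an inert low dose worse

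*SAP*

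**What the plan says.** - **Display.** SAP 8.6 plans "Descriptive summaries will be presented for each treatment group, BW strata, and all BW strata combined", and specifies the last of these "by all BW strata combined for STP206 low dose, STP206 high dose and control group". SAP 8.6.2.1 repeats this for NEC, sepsis, feeding intolerance, hospital death and complications of prematurity. SAP 8.7 repeats it for safety.
- **Statistic.** Categorical outcomes are shown as frequencies and percentages. Covariate adjustment (SAP 7.2) is "Not applicable to this study". No weighted or stratified estimate appears in the SAP.
- **Allocation.** SAP 4.3 states that "randomization will be stratified by BW in four strata". Each stratum has a low-dose cohort followed by a high-dose cohort, each of about 12 infants randomised 2:1.
- **Path to imbalance.** If the DSMC judges the high dose unsafe or poorly tolerated, "weight de-escalation will continue with the low dose of STP206" (SAP 4.1; protocol 7.1 agrees). Protocol 14.2 also lets the sponsor end the study, for example for slow enrolment.
- **Gap.** Neither document says how the combined dose columns are to be built or read if a high-dose cohort never opens.

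**The concern.** The combined columns carry a fair dose comparison only while low, high and control share the same birth-weight mix. Sequential opening, heaviest stratum first and low dose before high, means any early stop to the high dose removes it from the lightest infants. Those infants stay in the low and control columns.

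Protocol 5.1 says infants below 1500 g are at highest risk of NEC. A change of mix would therefore appear as a dose effect, in opposite directions for the two doses.

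Safety is the stronger reason to act. The primary objective is the safety of two dose levels against control, and the foreseen reason for dropping the high dose is a safety or tolerability finding. Its combined adverse-event column would then hold only the heavier infants. Those infants are generally of later gestation, because small-for-gestational-age infants are excluded. They are therefore dosed for less time (protocol Table 2, 2 to 11 weeks) and observed for less time, since adverse events are counted to six months after the last dose. The combined safety tables could flatter the dose that was withdrawn.

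**Working it through.** **Inputs from the documents.** There are eight cohorts of 12 infants randomised 2:1, so 8 STP206 and 4 control per cohort (protocol 7.1). NEC occurs in about 10% of VLBW infants (protocol 5.1). No stratum-specific risks are given.

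**The plan's own figure.** 8 × 12 = 96 infants, or 32 low, 32 high and 32 control. The stated 100 to 110 allows for non-evaluable infants at an unstated rate: 96/0.96 = 100 and 96/0.87 ≈ 110. The documents give no figure for the combined comparison.

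**Infants per column**, heaviest to lightest stratum:

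| Path | Low | High | Control |
|---|---|---|---|
| All eight complete | 8/8/8/8 = 32 | 8/8/8/8 = 32 | 8/8/8/8 = 32 |
| High dropped after 1b | 8/8/8/8 = 32 | 8/0/0/0 = 8 | 8/4/4/4 = 20 |
| High dropped after 2b | 8/8/8/8 = 32 | 8/8/0/0 = 16 | 8/8/4/4 = 24 |
| High dropped after 3b | 8/8/8/8 = 32 | 8/8/8/0 = 24 | 8/8/8/4 = 28 |
| Study stops after 3a | 8/8/8/0 = 24 | 8/8/0/0 = 16 | 8/8/4/0 = 20 |

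**Formula.** Expected crude column rate = Σ nₛpₛ / Σ nₛ, with the same stratum risks pₛ in every arm (no drug effect).

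**Example: high dose dropped after 2b, assumed risks 2/5/10/15%.**
- High: (0.16 + 0.40)/16 = 0.56/16 = 3.5%
- Control: (0.16 + 0.40 + 0.40 + 0.60)/24 = 1.56/24 = 6.5%
- Low: (0.16 + 0.40 + 0.80 + 1.20)/32 = 2.56/32 = 8.0%
- High v control RR = 3.5/6.5 = 0.54; low v control RR = 8.0/6.5 = 1.23

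**Crude high v control RR under no effect:**

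| NEC risk, heaviest to lightest stratum | After 1b | After 2b | After 3b |
|---|---|---|---|
| Flat 10% | 1.00 | 1.00 | 1.00 |
| Documents' 10% in the three lighter strata, 5% assumed above | 0.63 | 0.90 | 0.97 |
| Documents' 10% in the three lighter strata, 2% assumed above | 0.29 | 0.82 | 0.95 |
| Assumed 6/8/10/12% | 0.71 | 0.84 | 0.93 |
| Assumed 2/5/10/15% | 0.29 | 0.54 | 0.81 |
| Assumed 1/5/12/20% | 0.13 | 0.41 | 0.75 |

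At 2/5/10/15%, low v control RR is 1.18, 1.23 and 1.14. If the study stops after 3a, high is 3.5% and control (0.56 + 0.40)/20 = 4.8%, RR 0.73.

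**What is not affected.** With all eight cohorts complete, every RR is 1.00. Any-STP206 v control keeps 2:1 in each stratum. After 2b it is 16/16/8/8 v 8/8/4/4, giving (0.56 + 2.56)/48 = 6.5% in both, RR 1.00.

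**Chance.** By exact calculation for a drop after 2b at 2/5/10/15%, the high column falls below control with probability 0.62 and above it with probability 0.26. Two-sided Fisher p ≤ 0.05 favouring an inert high dose stays below 0.3% for NEC at every drop point. For a commoner event (assumed 10/20/40/60%) it is 2.5% to 7.0%, against 0.8% if all cohorts complete.

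**After correction.** The Mantel-Haenszel RR over birth-weight strata is 1.00 for both doses at every drop point and every gradient. For the high dose, restriction to opened strata is enough: 8/8 v 8/8 after 2b. For the low dose it is not. All four of its strata are open, so 8/8/8/8 v 8/8/4/4 remains and only stratum weighting restores 1.00.

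**Zero events.** After a 2b drop the restricted comparison is 16 v 16. The chance of no NEC in either arm at 2/5/10/15% is (0.98⁸ × 0.95⁸)² = 32%. After 1b it is 0.98¹⁶ = 72%. The usual Mantel-Haenszel interval then has zero width.

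**The case against.** On the planned path there is no bias. The secondary objectives and protocol 13.2.3.1 compare STP206 with control, and that contrast holds on every path examined. A shifted mix would also be visible: tables by stratum are always produced, disposition is shown by dose and stratum, birth weight is summarised for the same combined columns, and a DSMC decision on the high dose would be known. The plan is descriptive and exploratory, with no statistically derived sample size. All of this stands and limits the consequence.

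It does not remove the defect. By-stratum columns hold about 8 infants each. Seeing that the mix differs does not supply a fair dose comparison, and exploratory status does not correct a confounded percentage.

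Several stronger readings are tempting and are not supported:
- **That the combined columns are biased as planned.** They are not if all eight cohorts fill equally.
- **That RR 0.54 is the size of the problem.** The documents give the direction of the NEC gradient, not its size.
- **That this is the only view with more than eight infants per arm.** Tables 14.2.2.8 and 14.3.1.2.7 also pool strata, split at 28 weeks' gestation. They too are crude and separate the mix only in part.
- **That replacements upset the mix.** SAP 7.3 gives a replacement the assignment of the infant replaced. Both stay in the ITT and safety analyses, but no effect on the mix has been quantified.
- **That including infants of 1501–2000 g is an error.** They lie outside the stated target for clinical use but are enrolled by design. With complete cohorts their inclusion biases no contrast.

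**Conclusion.** The concern holds as a conditional one. If the high dose is dropped part-way, or the study stops between a low- and a high-dose cohort, the crude combined dose columns are expected to show an inert high dose as better than control and an inert low dose as worse.

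The shift is largest after stratum 1 and small after stratum 3. For a drop after stratum 2 the high-versus-control RR ranges from 0.41 at the steepest assumed gradient to 1.00 under flat risk. The risks closest to the documents give 0.82 to 0.90. These figures assume equal cohort filling and exact 2:1 allocation.

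For sepsis, death and adverse events the same direction requires that risk or observation time rises as birth weight falls. The documents make that plausible but do not quantify it. For NEC the harm is a misleading percentage, not a false significant finding.

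**What to change.** In SAP 7.2, 8.6 (with 8.6.2.1) and 8.7, before database lock and before dose-specific results are seen:

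1. For each dose versus control, build the combined comparison only from strata in which that dose was opened, with the controls of those strata.
2. Beside the counts, add a birth-weight-stratified (Mantel-Haenszel weighted) risk difference for NEC, death, sepsis and the overall TEAE and SAE summaries, labelled exploratory. Give it a stratified score-type interval, such as stratified Miettinen-Nurminen, that stays valid with zero events.
3. Show the number of infants per stratum in each combined column.
4. State that crude dose columns are not to be compared if any cohort was not opened.

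A combined NEC row for infants of 1500 g or less is optional and not part of the correction. The cost is SAP wording, a few table columns and some programming, with no new data. Intervals will be wide at these numbers.
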